9.0 STUDY CALENDAR

9.1 Pembrolizumab (MK-3475) Adjuvant Arm

REQUIRED STUDIES	Pre-Study	STEP 1: Random- ization	STEP 2: Surgery *	STEP 3: ADJUVANT PEMBROLIZUMAB (MK-3475) ON TREATMENT Infusions to be given q 3 weeks (+/- 3 days) for 18 total infusions						End of Treatment Assessment	Off treatment F/U prior to progression/ relapse ^c	F/U post relapse ^d
				C1	C2	C3	C4	C5	C6 ^g			
PHYSICAL												
History, PS & Physical ^a (w/BP, Height & Weight) ^t	X			X	X	X	X	X	X	X	X	
Toxicity Notation ^h	X			X	X	X	X	X	X	X	X	X
LABORATORY ^e												
CBC with Diff, Comprehensive Metabolic Panel ^a	X			X	X	X	X	X	X	X		
LDH	X											X
TSH, Free T ₄ ^o	X											
Pregnancy Test ⁱ	X			X	X	X	X	X	X			
Cardiac Function ^v												
X-RAYS AND SCANS	Please refer to footnotes j and k for details on the timing of scans.											
CT neck ^j , chest, abdomen & pelvis ^k	X											
Brain MRI or CT with contrast ^l	X											

Study Calendar 9.1 continued on next page. Click here for [footnotes](#).

REQUIRED STUDIES	Pre-Study	STEP 1: Randomi- zation	STEP 2: Surgery *	STEP 3: ADJUVANT PEMBROLIZUMAB (MK-3475) ON TREATMENT Infusions to be given q 3 weeks (+/- 3 days) for 18 total infusions						End of Treatment Assessment	Off treatment F/U prior to progressio n / relapse ^c	F/U post relapse ^d
				C1	C2	C3	C4	C5	C6 ^g			
SPECIMEN SUBMISSION												
Tissue ^{m,n} for banking				X								X
Whole Blood for banking _{m,n}				X				X		X		X
TREATMENT												
Surgical Resection			X									
pembrolizumab (MK-3475)				X	X	X	X	X	X	X		

Click here for [footnotes](#).

NOTE: Forms are found on www.ctsu.gov. Form submission guidelines are found in [Section 14.0](#).

NOTE: Unless indicated otherwise in the protocol, scheduled procedures and assessments (treatment administration, toxicity assessment for continuous treatment, disease assessment, specimen collection and follow-up activities) must follow the established SWOG guidelines as outlined in https://www.swog.org/sites/default/files/docs/2019-06/Best%20Practices_6.19.pdf.

CLOSED EFFICACY

9.2 Pembrolizumab (MK-3475) Neoadjuvant Arm

REQUIRED STUDIES	Pre-Study	ON TREATMENT ^a Infusions to be given q 3 weeks (+/- 3 days) for 18 total infusions									End of treatment assessment	Off treatment F/U prior to progression/relapse ^c	F/U post progression/relapse ^d
		STEP 1: NEOADJUVANT pembrolizumab (MK-3475)			STEP 2: SURGERY **	STEP 3: ADJUVANT MK-3475 (PEMBROLIZUMAB)							
PHYSICAL		C1	C2	C3	Surgery	C 4	C 5	C 6	C 7	C8	C18		
History, PS, & Physical ^a (w/BP, Height & Weight) ^t	X	X	X	X		X	X	X	X	X	X	X	
Toxicity Notation ^h	X	X	X	X		X	X	X	X	X	X	X	X
LABORATORY ^e													
CBC with Diff, Comprehensive Metabolic Panel ^a	X	X	X	X		X	X	X	X	X	X		
LDH	X												X
TSH, Free T ₄ ^o	X												
Pregnancy Test ⁱ	X	X	X	X		X	X	X	X	X			
Cardiac Function ^y													
X-RAYS AND SCANS	Please refer to footnotes j and k for details on the timing of scans.												
CT neck ^j , chest, abdomen & pelvis ^q	X				X ^q								
Brain MRI or CT with contrast ^{q, l}	X												

Study Calendar 9.2 continued on next page. Click here for [footnotes](#).
9.2 Pembrolizumab (MK-3475) Neoadjuvant Arm (contd.)

REQUIRED STUDIES	Pre-Study	ON TREATMENT Infusions to be given q 3 weeks (+/- 3 days) for 18 total infusions ^w									End of treatment assessment	Off treatment F/U prior to progression/relapse ^c	F/U post progression/relapse ^d
		STEP 1: NEOADJUVANT pembrolizumab (MK-3475)			STEP 2: SURGERY **	STEP 3: ADJUVANT PEMBROLIZUMAB (MK-3475)							
		C1	C2	C3	Surgery	C4	C5	C6 ^g	C7	C8	C18		
SPECIMEN SUBMISSION													
Tissue for assessing Pathologic Response					X								
Tissue ^{m,n} for banking		X											X
Whole Blood for banking ^{m,n}		X					X				X		X
TREATMENT													
MK-3475 ^w (pembrolizumab)		X	X	X		X	X	X	X	X	X		
Surgical Resection					X								

Click here for [footnotes](#).

NOTE: : Forms are found on www.ctsu.gov. Form submission guidelines are found in [Section 14.0](#).

NOTE: Unless indicated otherwise in the protocol, scheduled procedures and assessments (treatment administration, toxicity assessment for continuous treatment, disease assessment, specimen collection and follow-up activities) must follow the established SWOG guidelines as outlined in

https://www.swog.org/sites/default/files/docs/2019-06/Best%20Practices_6.19.pdf.

Footnotes for Study Calendars

- * Participants on Adjuvant arm must be registered to Step 2 (Surgery) within 17 days (preferably within 14 days) after randomization and must undergo surgical resection within 17 days (preferably within 14 days) after Step 2 registration. Interval between surgery and start of adjuvant therapy must not exceed 84 days.
 - ** Participants on Neoadjuvant arm should: receive 3 doses of neoadjuvant (pre-operative) pembrolizumab (MK-3475) prior to registration to Step 2; arrange surgery before registration to Step 2; and register to Step 2 within 4 weeks after the last neoadjuvant dose of pembrolizumab (MK-3475). Administration of less than 3 doses of pre-operative pembrolizumab (MK-3475) must be discussed with the Study Chair for approval.
- a. Following exams & labs are performed prior to receiving first dose and prior to every cycle until end of protocol treatment: physical (including BP & WT), PS, toxicity notation, CBC with differential (including ANC) and Comprehensive Metabolic Panel (Na, K, HCO₃ or CO₂, Serum creatinine or CrCl, non-fasting glucose, albumin, total bilirubin, AST, ALT, alkaline phosphatase).
 - c. Post-treatment follow-up (prior to relapse): Participants should be seen at 3 weeks (-/+ 1 week) after the last dose, then 12 weeks (-/+ 1 week) after the last dose, then every 3 months (+/- 2 weeks) if participant is < 2 years from study entry, every 6 months (+/- 4 weeks) if participant is 2-5 years from study entry, and every 12 months (+/- 4 weeks) if participant is > 5 years from study entry for up to 10 years. The first two follow-up visits may be scheduled to allow follow-up visits and scans to occur on the same date for on-going follow-up. The following exams and labs should be performed: physical (including BP & wt), and PS. For post-treatment follow-up regarding scans, see footnote [k](#).
 - d. Follow-up post progression/relapse: Participants who develop recurrent melanoma or who have progression of disease such that the participant cannot receive their planned surgery or require additional surgery will be followed for survival (vital status). Participants should be followed every 6 months for up to 2 years from the date of progression/relapse, then annually thereafter until 10 years from treatment randomization.
 - e. While on study, blood collected for pretreatment laboratory tests must be collected and analyzed no more than 3 days prior to dosing. NOTE: if pembrolizumab (MK-3475) was delayed per the dose delay/scheduling criteria or if a visit had to be delayed due to major circumstances (such as a health emergency, family/personal emergency, transportation difficulties, scheduling difficulties; a visit date falls on a holiday), the study assessments scheduled for these dates will be delayed.
 - g. Treatment and visits should continue at these intervals through Cycle 18.
 - h. Adverse Event Assessments on the study will continue for all participants until 30 days after the last study drug administration. However, participants with ongoing toxicities should be seen more often as clinically indicated.
 - i. Women of child bearing potential must have a negative serum or urine pregnancy test at screening within 28 days prior to randomization. Following randomization, serum or urine pregnancy tests are required within 72 hours prior to the first dose of study treatment, then according to institutional practice during therapy. Tests should coincide with clinic visits for blood work and ending with the discontinuation of study treatment. A pregnancy test should be done at any time there are clinical concerns for possible pregnancy.
 - j. Participants with primary melanoma of the head and neck or unknown primary with disease in the axilla will also require a neck CT.
 - k. Disease assessments by CT chest/abdomen/pelvis (or MRI if CT cannot be done), and neck CT as needed will be performed within 42 days (+/- 1 week) before surgery, and every 12 weeks (+/- 2 weeks) from the start of Adjuvant therapy until 2 years from randomization, then every 6 months (\pm 4 weeks) until 5 years from randomization, then follow for survival. In the case of a variation in scan schedule due to early or missed or delayed scans, the following scan is to be scheduled at the appropriate interval from the date of prior scan. If the interval between scans and Adjuvant therapy exceeds 42 days, repeat imaging must be obtained. The same imaging modality as used at prestudy for disease assessment should be used throughout the trial. If there is a contra-indication to iodine, non-contrast chest CT and MRI of abdomen/pelvis with gadolinium are acceptable body imaging alternatives. Extremity melanomas must be imaged using CT with intravenous contrast or MRI with and without gadolinium.

Note: PET-CT scans are NOT acceptable to establish eligibility.

(k. continued)

NOTE: If the disease assessment was completed within the last 42 days between the post-cycle 3 scan and registration for Step 3 (Adjuvant therapy), scans do not need to be repeated. If more than 42 days have elapsed between the post-cycle 3 scan and registration for Step 3 (Adjuvant therapy), scans must be repeated.

- l. During treatment and follow-up (through year 5), brain MRI/CT must be repeated annually (\pm 4 weeks); for years 6 through 10, brain MRI/CT to be performed annually as clinically indicated. If there is a gadolinium allergy, or MRI brain intolerable for the participant, CT with iodinated IV contrast is adequate brain imaging. Brain imaging is required for participants with progressive disease.
- m. If participant consents, submit specimens for banking as specified in [Section 15.2](#).
- n. Blood needs to be drawn prior to treatment.
- o. TSH (with a reflex to free T4) to be done at baseline on the same day of treatment (but prior to administration) and then as clinically indicated while on protocol treatment.
- q. Neoadjuvant participants must undergo disease assessments and tumor measurements via RECIST 1.1 at baseline and after the 3rd pre-operative dose/before Surgery (Weeks 7-12, timing per site discretion). Disease assessments then occur every 12 weeks thereafter until 2 years from randomization, then every 6 months (\pm 4 weeks) until 5 years from randomization, then follow for survival. In the case of a variation in scan schedule due to early or missed or delayed scans, the following scan is to be scheduled at the appropriate interval from the date of prior total body scan. If the interval between scans and the start of Adjuvant therapy exceeds 42 days, repeat imaging must be obtained. The same imaging modality as used at prestudy for disease assessment should be used throughout the trial. If there is a contra-indication to iodine, non-contrast chest CT and MRI of abdomen/pelvis with gadolinium are acceptable body imaging alternatives. Extremity melanomas must be imaged using CT with intravenous contrast or MRI with and without gadolinium.
- t. History prior to each treatment initiation to include a menstrual, sexual and contraceptive use history, including date of last menstrual period (for women of childbearing potential) which will help determine the need for pregnancy testing. Similar questions regarding contraceptive use to be asked of men who are sexually active with women of childbearing potential. Height is only required at baseline.
- v. Participants with history of CHF or who are deemed at risk because of underlying cardiovascular disease or exposure to cardiotoxic drugs should have an ECHO prior to treatment and an ECHO and EKG at the start of each cycle, as clinically indicated. Participants who have evidence at baseline (or subsequently) of CHF, MI, cardiomyopathy, or myositis cardiac evaluation (NYHA I/II) should have additional consult by a cardiologist, including review of EKG, CPK, troponin, ECHO cardiogram, as clinically indicated.
- w. Neoadjuvant Arm: pembrolizumab (MK-3475) 200 mg flat dosing IV every 3 weeks for 3 doses followed by surgical resection. Post-operative dosing every 3 weeks x 15 doses (18 doses total).

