1.0 OBJECTIVES

- 1.1 Primary Objective(s)
 - a. To compare event-free survival (EFS) in participants with high-risk resectable melanoma randomized to neoadjuvant pembrolizumab (MK-3475) with participants randomized to adjuvant pembrolizumab (MK-3475).
- 1.2 Secondary Objective(s)
 - a. To assess the frequency and severity of toxicities on each of the arms.
 - b. To compare between arms overall survival (OS), disease control at 24 weeks, locoregional control in the surgical site(s), and total number of pembrolizumab (MK-3475) doses received.
 - c. On the neoadjuvant arm, to estimate the pathologic response rate, the RECIST 1.1 response rate (confirmed and unconfirmed CR and PR), and the iRECIST response rate (confirmed and unconfirmed CR and PR), before surgical resection; to compare definitions of pathologic partial response; and to evaluate the association between pathologic response and EFS and OS.
 - d. To describe the proportion of participants on each arm who received the surgery planned at randomization.
- 1.3 Additional Objective(s)
 - a. To bank tumor tissue and whole blood in anticipation of future correlative studies in this participant population. Such proposed analysis includes deep immune profiling, with evaluation of CD3, CD8, PD-L1, CD20, whole exome sequencing studies, and RNA analysis.

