7.4 Follow-Up Disease Assessment Schedule

The same imaging modality as used at prestudy for disease assessment (see [Section 5.1.c](#)) must be used throughout the study.

For CT imaging, iodinated contrast is recommended in addition to FDG for optimal relapse detection. If there is a contra-indication to iodine, non-contrast chest CT and MRI of abdomen/pelvis with gadolinium are acceptable body imaging alternatives. Extremity melanomas must be imaged using CT with intravenous contrast or MRI with and without gadolinium.

Neoadjuvant participants must undergo disease assessments after the 3rd pre-operative dose/before surgery (Weeks 7-12, timing per site discretion). Disease assessments then occur every 12 weeks thereafter until participant receives surgery or has progression of disease before surgery such that the participant cannot receive the planned surgery.

Following surgery, disease-free status must be documented within 42 days prior to step 3 registration, using the same modalities as prestudy. If the interval between scans and Adjuvant therapy exceeds 42 days, repeat imaging must be obtained.

Disease assessments will then continue every 12 weeks (+/- 2 weeks) until relapse or 2 years from randomization and timed from prior imaging. Participants who are still relapse-free will then have disease assessments performed every 6 months (\pm 4 weeks) until relapse or 5 years from randomization.

In the case of a variation in scan schedule due to early or missed or delayed scans, the subsequent scan is to be scheduled at the appropriate interval from the date of prior total body scan.

During treatment and follow-up (through year 5), brain MRI/CT must be **repeated annually (\pm 4 weeks)**; for years 6 through 10, brain MRI/CT to be performed annually as clinically indicated. If there is a gadolinium allergy, or MRI brain intolerable for the participant, CT with iodinated IV contrast is adequate brain imaging. Brain imaging is required for participants with progressive disease.

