10.11 Length of disease control

Measured from date of randomization to date of the first of the following events: progression such that the participant cannot receive protocol surgery, protocol surgery that does not render the participant disease-free, relapse after surgery that did render a participant disease-free, death due to any cause; participants last known to be alive without any of these events will be censored at the date of last contact.

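### Section 7.4 and calendar footnotes k and q start the 12-weekly scans at three different points, none of them randomization, so the 24-week disease-control comparison rests on unequal scan histories; the effect is small

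*Combined protocol and SAP*

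**What the plan says.** Three rules govern the scans up to 2 years.

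- **Footnote k** to the Study Calendars: "every 12 weeks (+/- 2 weeks) from the start of Adjuvant therapy until 2 years from randomization".
- **Section 7.4**, after the disease-free imaging that precedes Step 3: "Disease assessments will then continue every 12 weeks (+/- 2 weeks) until relapse or 2 years from randomization and timed from prior imaging".
- **Footnote q** (neoadjuvant arm): a scan "after the 3rd pre-operative dose/before Surgery (Weeks 7-12, timing per site discretion"), and then "Disease assessments then occur every 12 weeks thereafter until 2 years from randomization".

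Calendar 9.2 marks its CT row with q, but the line above that row says "Please refer to footnotes j and k for details on the timing of scans". Footnote c sends post-treatment scan follow-up to k as well. Randomization fixes the change to 6-monthly scans at 2 years and the end of scanning at 5 years. It does not fix where the 12-week grid begins.

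Objective 1.2b compares "disease control at 24 weeks" between arms. Section 10.11 defines length of disease control as "Measured from date of randomization to date of the first of the following events: progression such that the participant cannot receive protocol surgery", among other events. Section 11.4 analyses disease control by Kaplan-Meier, log-rank and Cox methods and specifies no week-24 estimate or assessment window.

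**The concern.** A comparison at a fixed time from randomization is fair only if both arms have been examined similarly by then. Here the scan clock depends on events that occur at different times in the two arms. Neoadjuvant surgery is later by design, so a clock that starts at adjuvant therapy reaches the first surveillance scan later in that arm. Which rule a neoadjuvant site follows moves the date again.

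There is also a gap in coverage. Under k, an adjuvant-arm participant who has surgery and never starts adjuvant therapy has no start date for scans. For event-free survival (EFS) this matters little, because Section 10.10 gives non-registrants an event at day 84. For disease control and loco-regional control (Sections 10.11 and 10.12) that participant remains at risk. Under q, the counterpart in the other arm is scanned every 12 weeks.

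At stake is the 24-week comparison in 1.2b: equal true relapse could show as unequal detected relapse.

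**Working it through.** The plan states no figure on this point to reproduce. The check is calendar arithmetic, followed by a sizing under the plan's own control model.

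**1. First surveillance scan at preferred or recommended timing (Section 7.2).** I assume the first neoadjuvant dose is given at randomization. Section 13.1 allows up to 14 days, which would move the neoadjuvant dates later by up to 2 weeks.

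- Adjuvant arm: Step 2 at day 14, surgery at day 14 + 14 = 28, adjuvant start at day 28 + 14 = 42. Under k: 42 + 84 = day 126, week 18 (window 16-20). Under 7.4, with the Step 3 scan between days 28 and 42: weeks 16-18.
- Neoadjuvant arm: third dose at day 42, surgery at day 42 + 21 = 63, adjuvant start at day 63 + 14 = 77. Under k: 77 + 84 = day 161, week 23 (window 21-25). Under q, with the pre-operative scan at weeks 7-9: weeks 19-21.

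Under k alone the arms differ by 23 - 18 = 5 weeks, and the neoadjuvant window straddles week 24.

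**2. First surveillance scan at the outer limits.**

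- Adjuvant arm: surgery at day 17 + 17 = 34, adjuvant start at day 34 + 84 = 118. Under k: day 202, week 28.9. Under 7.4: weeks 22.9-28.9.
- Neoadjuvant arm: surgery at week 12, adjuvant start at week 24. Under k: week 36. Under q: weeks 19-24.

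Within the neoadjuvant arm, k and q differ by 2-4 weeks at recommended timing and by 12-17 weeks at the limits.

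**3. True failure by week 24.** Section 11.2 assumes 60% long-term survivors and a 2-year median (104.357 weeks) in the rest:

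F(24) = 0.40 × [1 - exp(-ln 2 × 24 / 104.357)] = 5.9%.

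I apply this to both arms, so any difference in detected failures is an artefact.

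**4. Detected failure by week 24.** Relapse is recorded at the first scan after it occurs. Surgery is assumed on days 14-34 (adjuvant arm) and 50-70 (neoadjuvant arm), with footnote k in both arms and a scan window of ±2 weeks. The second column is the share with a first surveillance scan by week 24.

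| Surgery to adjuvant start | Scanned, adj v neo | Detected, adj v neo |
|---|---|---|
| 14-17 days | 100% v 78% | 4.5% v 4.9% |
| about 28 days | 100% v 36% | 4.8% v 4.1% |
| about 42 days | 95% v 5% | 5.2% v 3.7% |
| spread over 17-84 days | 64% v 13% | 4.5% v 4.2% |

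The 42-day row is the most sensitive to details. Other handling of the scan window and the Step 3 scan date gives up to 98% v 2% scanned and 5.2% v 3.4% detected.

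At fixed recommended dates, k in both arms gives 4.5% v 4.7%. With q in the neoadjuvant arm it is 4.5% v 5.1%, or 4.5% v 4.4% if the pre-operative scan is at week 12. With the adjuvant arm at its outer limit and q in the other arm, it is 3.6% v 4.9%.

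**5. Does one anchor remove the gap?** Section 7.4 applied alone in both arms, at about 42 days, still gives 5.2% v 3.8%. A common grid from randomization (weeks 12, 24, and so on) gives 4.3% v 4.3%. A week-24 scan with failures counted through week 26 gives about 5.9% v 5.9%.

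**6. Sampling error.** With 336 participants (168 per arm) and about 5% failing: SE = √(2 × 0.05 × 0.95 / 168) = 2.4 points. A 1.5-point artefact is 0.015 × 168 = 2.5 participants per arm.

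**7. Log-rank test.** Over 2,000 simulated trials per scenario (336 participants, 104 events, accrual assumed uniform over 130 weeks), the type I error at the nominal two-sided 15% level was 13.7-17.3% across anchor combinations and 15.8% with a common grid. The Monte Carlo SE is about 0.8 points each. The largest excess over the common grid, 17.3 - 15.8 = 1.5 points, is 1.3 times the SE of that difference (√2 × 0.8 = 1.1). The overall hazard ratio under identical relapse was 1.00-1.01.

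**The case against.** **The documents partly reconcile themselves.** After an early, missed or delayed scan, k and q both reset to the prior scan, as 7.4 does. Section 7.4 also ends the neoadjuvant pre-operative schedule at surgery, which could be read as limiting q. This stands in part. However, q as written runs to 2 years, and calendar 9.2 still points to both footnotes. Section 7.4 does not tie the clock to adjuvant therapy, but it sequences from the Step 3 scan, so the participant who never reaches Step 3 is still not clearly covered.

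**Scan-only detection overstates the effect.** Physical examination is due before every 3-week cycle, and Section 10.5 does not limit relapse to scheduled imaging. Disease-free imaging before Step 3 and the neoadjuvant Week 7-12 scan also come before week 24. This stands: the sizes above are upper-end.

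**The comparison is thinly specified.** The 24-week time appears only in 1.2b. That lowers the weight of the point, but it is also a reason to write the analysis down.

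**Stronger readings that a reader might infer:**

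- *The three anchors cause the imbalance.* Step 5 shows nearly the same gap under 7.4 alone. Most of it comes from later neoadjuvant surgery combined with a clock not tied to randomization.
- *One arm is hardly scanned by week 24, so the neoadjuvant arm is flattered.* That needs adjuvant therapy to start about 42 days after surgery. Section 7.2 recommends within 17 days, preferably 14, and there the difference is small and runs the other way, even under k alone.

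**Conclusion.** The conflict between 7.4, k and q is in the text, and so is the mismatch between a scan grid not started at randomization and an endpoint timed from it. The consequence is modest: about 0.1 to 1.5 points in detected failure at week 24 against a true 5.9%, with a sign that depends on the surgery-to-adjuvant interval and the footnote followed. At the recommended interval it is about 4.5% v 4.9%.

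These sizes assume identical relapse in both arms under the Section 11.2 control model, detection by scan only, and the surgery dates given above. They are smaller than the 2.4-point standard error. A reader might infer that the primary EFS comparison is biased because the same scans feed it; the simulated type I error and hazard ratio do not support that. This is a fault of clarity and comparability in one secondary comparison. It is worth correcting because it is avoidable and its direction cannot be predicted.

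**What to change.** 1. Reconcile 7.4, k and q into one surveillance clock for all randomized participants in both arms, whether or not adjuvant therapy starts. Count it from randomization so that both arms have an assessment around week 24. Point both calendars to that single rule.
2. State in Section 11.4 that the 1.2b comparison is the Kaplan-Meier estimate of disease control at week 24, with a stated assessment window: for example, failures found at the week-24 assessment, through week 26.

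The cost is wording in 7.4, the footnotes and 11.4; the number of scans is about unchanged. For some participants the first surveillance scan would come sooner than 12 weeks after the Step 3 scan. The prior-scan reset wording must be aligned with the common clock, or the grids will drift apart again. For participants already past week 24, the second step can still be taken, but it cannot supply a scan that was not done.

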10.10 Event-Free Survival

Measured from date of randomization to date of first: documentation of progression that renders participant unable to receive planned protocol surgery, off protocol therapy for any reason without subsequent protocol surgery (with one exception noted below), failure to begin adjuvant therapy within 84 days after surgery, relapse after surgery or death due to any cause. Participants last known to be alive and event-free are censored at date of last contact. On both arms, all participants who do not register for adjuvant therapy (for whatever reason) will be assigned the event time of 84 days.

Patients treated on the neo-adjuvant arm who achieve an unconfirmed PR or CR (per RECIST 1.1) at the first protocol disease assessment and choose not to undergo protocol surgery will not be counted as an event if the PR or CR is confirmed prior to starting any non-protocol therapy other than pembrolizumab. Such patients will not have an event when not receiving protocol surgery, and their EFS will be measured from the date of randomization to the first of relapse or death due to any causes with patients last known to be alive without relapse censored at the date of last contact. All other patients who do not receive protocol surgery will be assigned the EFS event time of 84 days.

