11.2 Analysis plan and sample size justification for primary objective

Based on EFS trends in this participant population, we will use exponential-mixture cure models to describe EFS patterns in the arms. Based on Weber 2017, we assume that on the adjuvant pembrolizumab (MK-3475) arm (null hypothesis) 60% participants will be long-term survivors (or cured or not observed to have an event during the finite follow-up of the trial) and that median EFS for participants who are not long-term survivors will be 2 years. We power this study to detect an alternative EFS in the neoadjuvant arm with 70% of participants being long-term survivors and median EFS among those who are not long-term survivors of 2.5 years. We note that these survival patterns do not follow a proportional hazards assumption and that average hazard ratios from Cox models are expected to become more null with additional follow-up.

We assume 1:1 randomization, accrual over 2 years, and up to 10 years of follow-up after randomization. Under these assumptions the average hazard ratio under the alternative is 0.64. Under the alternative, with a sample size of 500 eligible participants (250/arm), 100% of expected events is 104 events across both arms. At 50% of expected events (51 events, expected approximately when accrual completes), we will perform a futility test testing the alternative hazard ratio from a Cox regression model at the one-sided 2.5% level. No formal interim test of efficacy will be performed. Under the null hypothesis the probability of stopping early for futility is 45% and under the alternative is 2%. The final analysis will consist of a log-rank test of the null hypothesis at the two-sided 15% level (expected 1.5 years after accrual completes). The power of this design is 81%.

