11.3 Sample size re-design

Because accrual to the study has been slower than anticipated, it is expected that 100% of events may be reached before accrual to the study completes, and so the total sample size of the study will be adjusted as follows.

To account for the slower than anticipated accrual rate, a total of 336 eligible, randomized patients will be accrued. If up to 1.5% of patients are not eligible, up to 342 patients will be registered. With the same assumptions for EFS as in the original design, this design should have the same power as the original design using the same alpha. We expect to reach full events within 6 months of completing accrual.

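### After the cut to 336 patients, the plan's own EFS model reaches 104 events only about 5 years after accrual, partly after scheduled body scans end, and the final analysis has no calendar backstop

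*Combined protocol and SAP*

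**What the plan says.** **Event number and sample size.** Section 11.2 assumes a mixture cure model for EFS. On the adjuvant arm "60% participants will be long-term survivors", with a median of 2 years among the rest. The neoadjuvant alternative is 70% and 2.5 years. For 500 eligible patients and 2 years of accrual, it states that "100% of expected events is 104 events across both arms". The final log-rank test (two-sided 15%) is expected 1.5 years after accrual, with 81% power. Section 11.3 then says that "a total of 336 eligible, randomized patients will be accrued". It carries over the EFS assumptions, alpha and power, and expects full events within 6 months of the end of accrual. It does not restate the event number.

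**Disease assessment.** Section 7.4 schedules body imaging "until relapse or 5 years from randomization". Calendar footnotes k and q set the same limit: "until 5 years from randomization, then follow for survival". Footnote c keeps relapse-free participants on visits "every 12 months (+/- 4 weeks) if participant is > 5 years from study entry for up to 10 years", with physical examination and performance status.

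**Endpoint.** Section 10.10 sets no matching limit: "Participants last known to be alive and event-free are censored at date of last contact". Deaths count as events whenever they occur.

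**The concern.** The three parts no longer fit together after the re-design. With 500 patients, 104 events would arrive well before anyone ran out of scheduled scans. With 336 patients and the same model, the expected count at 5 years per participant is below 104, so under the alternative the last events needed come from follow-up without scheduled body imaging.

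Three things are at stake. The primary analysis could come years later than planned, or never reach its event number. The stated power may not be what the re-designed trial delivers. The late events would rest on less regular assessment than the rest. Nor does waiting help: Section 11.2 itself says that "average hazard ratios from Cox models are expected to become more null with additional follow-up".

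**Working it through.** **Inputs.** Cure fractions 60% and 70%, non-cured medians 2 and 2.5 years, 1:1 allocation, two-sided 15% log-rank test (Section 11.2); 336 patients, so 168 per arm (Section 11.3). Section 11.3 gives no accrual length, so 2 to 5 years of uniform accrual is assumed.

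**Model.** F(t) = (1 − c)(1 − 2^(−t/m)), with c the cure fraction and m the non-cured median. With uniform accrual over A years and analysis s years after accrual, the mean of F is (1 − c){1 − [m/(A ln 2)] [2^(−s/m) − 2^(−(s+A)/m)]}.

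**1. The plan's own figures (500 patients, A = 2, s = 1.5).**
- Adjuvant: 250 × 0.4 × {1 − 1.443 × (0.595 − 0.297)} = 57.1.
- Neoadjuvant: 250 × 0.3 × {1 − 1.803 × (0.660 − 0.379)} = 37.0.
- Total under the alternative: 94.1, not 104. Under the null it is 114.2. The mean of the two is 104.2, and the same mean at accrual end is 50.5 against the stated 51. So 104 looks like an average over both hypotheses, and its label should be checked.
- Power reproduces: 81.0% by simulation at 1.5 years after accrual.

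**2. Events with 168 per arm.**
- By year 5, alternative: 168 × 0.4 × (1 − 2^(−2.5)) + 168 × 0.3 × (1 − 2^(−2)) = 55.3 + 37.8 = 93.1.
- By year 10, alternative: 168 × (0.3875 + 0.28125) = 112.4.
- By year 5, null: 2 × 55.3 = 110.6.
- For comparison, 250 per arm under the alternative give 138.6 by year 5.

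**3. Timing under the alternative, 336 patients.**

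| Accrual (years, assumed) | Events 6 months after accrual | Years after accrual to 104 expected events |
|---|---|---|
| 2 | 43.2 | 5.9 |
| 3 | 52.7 | 5.5 |
| 4 | 60.5 | 5.1 |
| 5 | 67.0 | 4.7 |

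At the 104th expected event, 104 − 93.1 = 10.9 events lie beyond 5 years from randomization. With 500 patients and 2 years of accrual, 104 comes about 1.9 years after accrual, with essentially none beyond year 5. Under the null with 336 patients it comes 2.1 to 3.4 years after accrual, with 101 to 104 of the events inside 5 years.

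**4. Simulation under the alternative** (6,000 trials per setting, 51-event futility look, standard error about 0.5 point).

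| Design | Accrual (years) | Power | Mean hazard ratio |
|---|---|---|---|
| 500 patients, 1.5 years after accrual | 2 | 81.0% | 0.61 |
| 336, wait for 104 | 2 | 76.1% | 0.65 |
| 336, wait for 104 | 3.5 | 75.9% | 0.65 |
| 336, all followed and cut at 5 years | 2 | 77.7% | 0.63 |
| 336, all followed and cut at 5 years | 3.5 | 76.8% | 0.63 |

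When waiting for 104, 15 to 16% of trials never reach it within 10 years of follow-up. Power falls although the event number is unchanged, because the same events are gathered over longer follow-up, where the average hazard ratio is closer to 1.

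**5. Sensitivity to day-84 events.** Section 10.10 assigns an event at day 84 to participants who do not register for adjuvant therapy, with one exception for confirmed responders who decline surgery. If a fraction p of all participants has such an event in addition to the model, the 5-year total is 336p + 93.1(1 − p): 99 at 2.5%, 105 at 5%, 117 at 10%. It equals 104 at p = 10.9/242.9 = 4.5%.

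**The case against.** The strongest reply is that the imaging schedule is not the root of this. Section 11.3 expects full events soon after accrual, long before most participants reach year 5. If that forecast fails, the fault lies in pairing 336 patients with 104 events. This stands. A reader might infer that the 5-year scan limit is itself the error, but the limit was compatible with 500 patients and still is under the null.

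A reader might also infer that the primary analysis must wait on unscanned time. The documents do not support that as a certainty. The number 104 is carried over by inference, and about 4.5% extra day-84 events would remove the shortfall. Section 11.5 suspends accrual only above 16% unresectable or 5% unfit for surgery through toxicity on the neoadjuvant arm, so losses of that order are contemplated.

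Nor does the text support the inference that only symptomatic relapse or death is found after year 5. Annual examination continues to year 10 and can find asymptomatic nodal or skin relapse. Brain imaging continues as clinically indicated. Section 14.3 asks for yearly follow-up forms through year 10, and for relapse reports with no 5-year limit. Ascertainment is reduced, not absent. Section 10.2 does, however, treat whole-body scanning at set intervals as needed when progression is an endpoint.

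The scan limit is the same in both arms, and no type I error effect has been shown. The data monitoring committee sees reports every 6 months and may decide on early reporting, so a stalled count would be noticed. That does not replace a stated rule for when the primary analysis takes place.

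**Conclusion.** The re-designed plan does not deliver its stated timing or power under its own assumptions. Under the alternative, 336 patients give about 93 events within the scheduled scan period. The 104th is expected 4.7 to 5.9 years after accrual rather than within 6 months, about 11 events fall after scheduled body imaging stops, and about 15% of trials never get there. Power is about 76 to 78% against 81%.

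This rests on the Section 11.2 cure model, on 104 still being the full-event number, and on the assumed 2 to 5 years of accrual. The 6-month forecast fails even if 94 was the number meant, since 43 to 67 events are expected then.

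It is tempting to conclude that EFS should be censored at the last scan. The calculations do not require it: ending at 5 years neither loses nor materially gains power, and censoring at the last scan would discard deaths that Section 10.10 counts.

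**What to change.** In Sections 11.2 and 11.3:
- State the full-event number for 336 patients, and correct or explain the label on 104.
- Trigger the final analysis at that number or when the last participant reaches 5 years from randomization, whichever is first.
- Restate the expected events at that point (about 93 within 5 years of randomization under the alternative), the power (about 77%) and the timing. Counting all events by the backstop date, the accrual formula with s = 5 gives 99, 102, 104 and 105 for accrual of 2, 3, 4 and 5 years. If 104 is kept, the backstop would therefore usually act when accrual is short.

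Leave the primary EFS definition in Section 10.10 as it is, so that all deaths still count. Add a sensitivity analysis that truncates EFS at 5 years from randomization.

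The cost is wording, plus a stated power and event number slightly less favourable than now. No extra scans or patients are needed, and simulated power is no lower than when waiting for 104 events.
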